5.1.1 Retesting During Screening or Lead-in Period

Retesting of laboratory parameters and/or other assessments within any single Screening or Lead-in period will be permitted (in addition to any parameters that require a confirmatory value).

Any new result will override the previous result and is the value by which study inclusion will be assessed, as it represents the subject's most current, clinical state.

Laboratory parameters and/or assessments that are included in [Table 5.1-1](#), Screening Procedural Outline may be repeated in an effort to find all possible well-qualified subjects. Consultation with the Medical Monitor may be needed to identify whether repeat testing of any particular parameter is clinically relevant.

5.2 Study Materials

- NCI CTCAE version 4.03
- Nivolumab IB
- Brentuximab Vedotin IB
- Pharmacy Binder
- Laboratory manuals for collection and handling of blood (including PKs, biomarker and immunogenicity) and tissue specimens
- Site manual for operation of IVRS, including enrollment worksheet
- Manual for submission of local laboratory data
- Serious Adverse Events (or eSAE) case report forms
- EQ-5D 3L questionnaires
- Pregnancy Surveillance Forms

5.3 Safety Assessments

At baseline, a medical history will be obtained to capture relevant underlying conditions. The baseline examinations should include weight, height, ECOG Performance Status, blood pressure (BP), heart rate (HR), temperature, and oxygen saturation by pulse oximetry at rest (also monitor amount of supplemental oxygen if applicable) and should be performed within 28 days prior to first dose.

Physical examination will be performed as clinically indicated and clinical signs and symptoms are to be collected within 14 days of first dose. For subjects with CTCL, a skin examination following the mSWAT should be included. During the on-treatment visits, a target physical examination is acceptable and it should include the assessment of the lymph node areas, abdominal organs (eg, spleen), neurological assessment and skin lesions if applicable. If there are any new or worsening clinically significant changes since the last exam, report changes on the appropriate non-serious or serious adverse event page.

Pregnancy testing (urine or serum) must be done in WOCBP only and within 24 hours of first dose and at least every 4 weeks (+/- 3days) thereafter regardless of dosing schedule.

Baseline local laboratory assessments must be done within 14 days prior to first dose to include CBC w/differential, LFTs (ALT, AST, total bilirubin, alkaline phosphatase), BUN or serum urea level, creatinine, uric acid, Ca, Mg, Na, K, Cl, LDH, glucose, albumin, amylase, lipase and urinalysis (total protein, glucose blood, leukocyte esterase, specific gravity and pH).

Baseline local laboratory assessments for Hep B and C testing (HBV sAg, HCV Ab or HCV RNA) must be done within 28 days prior to first dose.

On treatment oxygen saturation by pulse oximetry should be obtained within 72 hours prior to dosing and at any time a subject has any new or worsening respiratory symptoms. A reading at rest should be obtained at each time point. If a subject shows changes on pulse oximetry or other pulmonary-related signs (eg, hypoxia, fever) or symptoms (eg, dyspnea, cough) consistent with possible pulmonary adverse events, the subject should be immediately evaluated to rule out pulmonary toxicity. An algorithm for the management of suspected pulmonary toxicity can be found in [Appendix 6](#) and the nivolumab IB.

Thyroid function testing is to be done at every other cycle (approximately every 6 weeks, unless treatment delays are observed) for subjects receiving study drug. At baseline TSH, Free T3 and Free T4 will be performed within 14 days of first dose. During treatment TSH will be done (with reflexive Free T4 and Free T3 if TSH results are abnormal) within 72 hours prior to dosing.

On treatment local laboratory assessments should be done within 72 hours prior to dosing; and will include CBC with differential, BUN or serum urea level, serum creatinine, sodium, potassium, calcium, magnesium, chloride, amylase, lipase, glucose, AST, ALT, total bilirubin, alkaline phosphatase and LDH.

Local laboratory assessments are to be performed for the Follow-up X01 visit and include CBC with differential, uric acid, serum urea level, uric acid, albumin, creatinine, sodium, potassium, calcium, magnesium, chloride, glucose, AST, ALT, total bilirubin, alkaline phosphatase, LDH, TSH (reflex to free T3, free T4 for abnormal TSH result). This panel should be repeated at Follow-up visit X02 if Follow-up visit X01 results were abnormal.

For subjects who discontinue study therapy by proceeding to allogeneic SCT, documentation of acute and chronic GVHD will be captured on **Day 100, at 6 months, 1 year and every year thereafter from the date of stem cell infusion** until the first non-CR after SCT is documented.

Subjects will be evaluated for safety if they have received any study drug. Toxicity assessments will be continuous during the treatment phase. During the Follow-Up Phase at Visits X01 and X02, toxicity assessments should be done in person. Follow-up visit 1 (X01) is to occur 35 days from the last dose +/- 7 days. Follow-up visit 2 (X02) is to occur 80 days (+/- 7 days) from follow-up visit X01. Once subjects reach the survival follow-up phase, either in-person visits or documented telephone calls/email correspondence to assess the subject's status are acceptable. Survival visits should occur every 3 months. BMS may request that survival data be collected on all treated

subjects outside of the 3 month specified window. At the time of this request, each subject will be contacted to determine their survival status unless the subject has withdrawn consent for all contact.

Adverse events and laboratory values will be graded according to the NCI-CTCAE version 4.03.

Additional measures, including non-study required laboratory tests, should be performed as clinically indicated or to comply with local regulations. Laboratory toxicities (eg, suspected drug induced liver enzyme evaluations) will be monitored during the follow-up phase via on site/local labs until all study drug related toxicities resolve, return to baseline, or are deemed irreversible.

Some of the assessments referred to in this section may not be captured as data in the eCRF. They are intended to be used as safety monitoring by the treating physician. Additional testing or assessments may be performed as clinically necessary or where required by institutional or local regulations.

5.3.1 Imaging Assessment for the Study

Any incidental findings of potential clinical relevance that are not directly associated with the objectives of the protocol should be evaluated and handled by the Study Investigator as per standard medical/clinical judgment.

At the sponsor's discretion, scans may be collected centrally to be reviewed by independent radiologists.

5.4 Efficacy Assessments

DLBCL, PTCL, PMBL and MGZL Efficacy Assessment:

The primary efficacy assessment is Objective Response (OR). Objective Response is defined as a subject achieving either a PR or CR according to the Lugano Classification 2014 and Lymphoma Response to Immunomodulatory therapy Criteria (LYRIC) ([Appendix 2](#)) and will be based on investigator assessed response. Efficacy assessment for DLBCL, PTCL, PMBL and MGZL will be primarily derived from the FDG PET-CT performed according to the timepoints described in [Table 5.1-1](#) [Table 5.1-2](#) and [Table 5.1-3](#). Subjects with PET-Avid lesions at baseline should be followed with PET, subjects with non-Pet avid lesions and lesions on CT scans at baseline should be followed with CT Scans. Tumor assessment (CR or non-CR) will be assessed by the investigator according to the Lugano Classification 2014.

CTCL Efficacy Assessment:

Efficacy assessment for Cutaneous T Cell lymphomas will include CT/MRI for visceral disease assessment and peripheral lymph nodes at the pre-determined timepoints described in [Table 5.1-1](#) [Table 5.1-2](#) and [Table 5.1-3](#). The consensus Global Response Score assessment to evaluate disease activity will also be completed at every tumor assessment time point to assess extent of disease. Medical photographs are recommended to document the appearance of skin lesions throughout the study. The mSWAT will be used to assess skin involvement, it is preferable that the mSWAT assessments should be performed by the same investigator at all time points to eliminate inter-

observer variability for a given patient. Lymphoma Response to Immunomodulatory therapy Criteria (LYRIC) will be used where clinically indicated ([Appendix 2](#)).

Whole blood must be included for assessment of SS-CTCL at baseline to evaluate blood tumor burden. In the case the blood is confirmed to be positive for tumor cells, it must be reassessed at the time of response documentation, prior to its confirmation.

All subjects treated are expected to be followed for disease progression. Subjects that discontinue treatment for other reasons different from disease progression must continue to perform tumor assessments as described in [Table 5.1-3](#) until disease progression is documented.

The primary analysis of the study will be performed 8 months after the last subject has received the first dose of study medication, or earlier if that subject discontinues study therapy. After the cut off for the primary analysis, subjects who are receiving study treatment can continue treatment per protocol until progression, unacceptable toxicity, withdrawal of consent, or other reasons as listed in [Section 3.5](#).

Once subjects discontinue study therapy by proceeding to allogeneic SCT or ASCT, they will not undergo radiographic assessments at the predetermined timepoints described in [Table 5.1-3](#). Instead, they will be evaluated on **Day 100, at 6 months, 1 year and every year thereafter from the date of stem cell infusion** until the first non-CR after SCT is documented.

Sites are required to have available on site all of the on-study tumor scans.

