All subjects in Cohort A and Cohort B will be allowed to be treated until disease progression or unacceptable toxicity as described in [Section 4.5.3](#) and [Section 4.5.5](#). If during therapy it appears that a subject is benefiting from the combination but experiencing toxicities related to one agent that would require permanent treatment discontinuation, then they have the option to continue therapy with the single agent not attributing to toxicities.

Subjects that present progressive disease during treatment may be allowed to be treated beyond progression until further progression is observed. Refer to [Section 4.5.9](#) for further details.

Once subjects discontinue from study treatment for any reason, subjects will enter the follow-up phase of the study. During follow-up, long-term safety, survival status, disease progression, subsequent anticancer therapy and occurrence of other primary malignancy data will be collected. Follow-up visit 1 (X01) and follow-up visit 2 (X02) will be in person visits and all subsequent follow-up visits may be done in person or by phone. All treated subjects will be followed for survival at least every 3 months until death or lost to follow-up. Subjects with residual toxicity $G \geq 2$ at the time of discontinuation must follow these until resolved to at least G1, end of study or deemed irreversible, whichever occurs first. Subjects who discontinue for reasons different than progressive disease must continue to perform tumor assessments as described in [Section 5.4](#) until disease progression is documented.

The primary endpoint for Cohort B will be investigator-assessed ORR for all five tumor types. This analysis will occur 8 months after the last patient receives their first treatment (LPFT). Depending on the enrollment for each disease cohort, the analysis may be done at different times for each cohort or at the same time for the five cohorts.

The study design schematic is presented below.

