follow-up visits may be done in person or by phone. All treated subjects will be followed for survival at least every 3 months until death or lost to follow-up. Subjects with residual toxicity G \geq 2 at the time of discontinuation must follow these until resolved to at least G1, end of study or deemed irreversible, whichever occurs first. Subjects who discontinue for reasons different than progressive disease must continue to perform tumor assessments as described in [Section 5.4](#) until disease progression is documented.

The primary endpoint for Cohort B will be investigator-assessed ORR for all five tumor types. Primary endpoint analysis will occur 8 months after the last patient receives their first treatment (LPFT). Depending on the enrollment for each disease cohort, the analysis may be done at different times for each cohort, or at the same time for the five cohorts. The study design schematic is presented in [Figure 3.1-1](#).

Figure 3.1-1: Study Design Schematic

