5.4.1 Radiographic Assessments

Baseline assessments should be performed within 28 days prior to the first dose, utilizing FDG PET-CT, CT or MRI. CT scans are preferred for CTCL. In addition to chest, abdomen, pelvis, all known sites of disease should be assessed at baseline. FDG PET-CT will be performed for assessment throughout the study for subjects with DLBCL, PTCL, PMBL and MGZL. Low dose or attenuation correction CT portions of a combined FDG PET-CT are of limited use in anatomically based efficacy assessments and it is therefore suggested that they should not be substituted for dedicated diagnostic contrast enhanced CT scans for anatomically based measurements. However, if a site can document that the CT performed as part of a FDG PET-CT is of identical diagnostic quality to a diagnostic CT with oral contrast, (+/- IV contrast) then the adequate dose CT of the FDG PET-CT can be used for tumor measurements. Subjects with CTCL are to perform the CT scans described above in addition to medical photographs if appropriate for disease assessment.

Subjects will be evaluated for tumor response by FDG PET-CT, or CT/MRI at week 6 and week 12 continuing every 9 weeks (+/- 1 week) for the subsequent 4 tumor assessment timepoints, regardless of dosing schedule. After the first year, tumor assessments are to occur every 12 weeks (+/- 2 weeks) until disease progression is documented.

Tumor assessments for ongoing study treatment decisions will be completed by the investigator using the Lugano Classification 2014 for Diffuse Large B Cell Lymphomas and Peripheral T Cell Lymphomas. Refer to [Appendix 2](#) for further details. For Cutaneous T Cell Lymphomas, response

should be assessed by the consensus Global Response Score. Refer to [Appendix 4](#) for further details.

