8.3 Endpoints

8.3.1 Primary Endpoint(s)

The primary safety endpoints include incidence of deaths, adverse events, serious adverse events, adverse events leading to discontinuation, adverse events leading to dose delay, drug-related adverse events and specific laboratory abnormalities (worst grade). Toxicities will be graded using the National Cancer Institute (NCI) Common Terminology Criteria for Adverse Events (CTCAE) version 4.03.

The primary efficacy endpoint is ORR. It is defined as the number of subjects with a best overall response (BOR) of confirmed CR or PR divided by the number of treated subjects. The BOR is defined as the best response designation recorded between the date of first dose and the date of initial objectively documented progression or the date of subsequent therapy, whichever occurs first. Allogeneic SCT and ASCT will be considered as subsequent therapy. In subjects with relapsed refractory DLBCL, relapsed refractory PTCL, relapsed refractory PMBL and relapsed refractory MGZL the response (CR, PR, PD, and progression) will be assessed according to Lugano Classification 2014. For subjects with relapsed refractory CTCL, response will be assessed according to consensus Global Response Score as per the consensus statement of the International Society for Cutaneous Lymphoma. A CR must have been confirmed by scans, including a negative Positron Emission Tomography (PET) to be considered for CR in subjects with PTCL, DLBCL, PMBL and MZGL. In subjects with PTCL, if the bone marrow was compromised at baseline, a bone marrow must also be negative at the time of CR. In CTCL CT scans (chest, neck, abdomen and pelvis), blood flow for SS cells and m SWAT skin scoring along with medical photography will be performed at baseline and at the end of the treatment for response evaluation. The investigator will perform tests that will allow evaluation of response to therapy according to corresponding disease criteria in [Appendix 2](#) and [Appendix 4](#). The analysis of the primary endpoint will occur approximately 8 months after the last enrolled subject's first dose of study therapy. Depending on the enrollment for each disease cohort, the analysis may be done at different times for each cohort, or at the same time for the three cohorts.

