Abbreviations: CR, complete response; NI, noninvolved; PR, partial response; PD, progressive disease; SD, stable disease.
*It is recommended that not only the proportion of patients who achieve a response or an unfavorable outcome be calculated but a life table account for the length of the interval during which each patient is under observation also be generated.

Response Evaluation in CTCL:

Response in CTCL will be evaluated based on the involvement of different sites (lymph nodes, viscera, skin and blood) using the TNMB staging (as clinically indicated) and will be incorporated in the Global Response Score. The m SWAT will be used for skin scoring.

All responses to be designated as CR or PR, should be documented for at least 4 weeks in duration. No CR can be ascribed to a study drug while a patient remains on concomitant therapy (such as topical steroids) with known efficacy in MF/SS.

In certain cases to document CR a biopsy may be required if there are limitations on Spiral CT scan or MRI examination for lymph node or viscera evaluation and if it is deemed necessary.

Blood evaluation for Sezary syndrome: The absolute number of CD4+ CD26- determined on flow cytometry will be used to assess blood involvement. A normal value for CD+ CD26- or CD4+CD7- cells by flow cytometry is lower than 15%.

Response in skin:

m SWAT for skin scoring/evaluation, to track skin tumor burden.

CR: 100% clearance of skin lesions.

PR: 50%-99% clearance of skin disease from baseline without new tumors (T3) in patients with T1, T2 or T4 only skin disease. ($\geq 50\%$ reduction in the mSWAT score compared with baseline).

Stable disease: $< 25\%$ increase to $< 50\%$ clearance in skin disease from baseline without new tumors (T3) in patients with T1, T2, or T4 only skin disease. (Less than 50% reduction to less than 25% increase in the mSWAT score compared with baseline).

Progressive disease: $> 25\%$ increase in skin disease from baseline or new tumors (T3) in patients with T1, T2 or T4 only skin disease or Loss of response: in those with complete or partial response, increase of skin score of greater than the sum of nadir plus 50% baseline score. Relapse is any disease recurrence in those with complete response. ($\geq 25\%$ increase in the mSWAT score from baseline).

Response in the lymph nodes will be assessed using a Spiral CT Scan or MRI.

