4 ENDPOINTS

4.1 **Primary Endpoints**

The primary safety endpoints include DLT, incidence of deaths, adverse events, serious adverse events, adverse events leading to discontinuation, adverse events leading to dose delay, drug-related adverse events and specific laboratory abnormalities (worst grade). Toxicities will be graded using the National Cancer Institute (NCI) Common Terminology Criteria for Adverse Events (CTCAE) version 4.03.

The primary efficacy endpoint is ORR. It is defined as the number of subjects with a best overall response (BOR) of CR or PR divided by the number of treated subjects. The BOR is defined as the best response designation recorded between the date of first dose and the date of initial objectively documented progression or the date of subsequent therapy, whichever occurs first. Allogeneic SCT and ASCT will be considered as subsequent therapy. In subjects with relapsed refractory DLBCL, relapsed refractory PMBL, relapsed refractory MGZL and relapsed refractory PTCL the response (CR, PR, SD and progression) will be assessed according to Lugano Classification 2014. A CR must have been confirmed by scans, including a negative Positron Emission Tomography (PET) to be considered for CR in subjects with PTCL, PMBL, MGZL and DLBCL. For subjects with relapsed refractory CTCL, response will be assessed according to consensus Global Response Score as per the consensus statement of the International Society for Cutaneous Lymphoma.

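### Protocol 5.4 lets the primary analysis run before 8 months if the last-treated subject stops therapy; the synopsis, 3.1 and 8.3.1 contain no such trigger, and it secures no minimum follow-up for response.

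*Protocol*

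**What the plan says.** Four places in the protocol time the primary analysis.

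- Synopsis, Study Design: "This analysis will occur 8 months after the last patient receives their first treatment (LPFT").
- Section 3.1: "Primary endpoint analysis will occur 8 months after the last patient receives their first treatment (LPFT").
- Section 8.3.1: "The analysis of the primary endpoint will occur approximately 8 months after the last enrolled" subject's first dose.
- Section 5.4: "8 months after the last subject has received the first dose of study medication, or earlier if that subject discontinues study therapy". The next sentence of 5.4 treats this as the cut-off for the primary analysis.

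Only 5.4 has an early trigger. The SAP sections available give no cut-off date (SAP Section 1 is not in the text available). SAP Section 9 says only that subtypes may be analysed at different times, as do Protocol 3.1 and 8.3.1.

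Other provisions that matter here:

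- Section 5.4 keeps assessments going after treatment ends: "Subjects that discontinue treatment for other reasons different from disease progression must continue to perform tumor assessments".
- Section 5.4.1: "Subjects will be evaluated for tumor response by FDG PET-CT, or CT/MRI at week 6 and week 12", then every 9 weeks for four more assessments.
- SAP 4.1 defines ORR as the number with a "best overall response (BOR) of CR or PR divided by the number of treated subjects". SAP 7.5.1 confirms that the primary ORR uses all treated subjects. Protocol 8.3.1 has the same denominator but asks for confirmed responses.

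**The concern.** The early clause makes the data lock for the primary endpoint depend on one subject's course. That subject stopping therapy is not a sign that response data are complete: a stop without progression leaves scanning in force, and other subjects treated shortly before may still be awaiting their first or best response. The clause sets no minimum follow-up for them and does not say how long after the stop the data are cut. It also leaves open whether the last subject is the last in the study or the last in each cohort.

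At stake are an unambiguous cut-off for the primary endpoint, an ORR estimate that may be biased downward, some power in small cohorts, and follow-up for DOR, PFS and OS. SAP 7.5.2 makes the 6- and 12-month PFS and OS rates depend on minimum follow-up. A fixed 8-month cut-off gives every treated subject potential follow-up beyond 6 months; the early trigger does not.

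**Working it through.** **1. The plan's own power figures.** Inputs from Protocol 8.1: cohort sizes, null and target ORRs, one-sided alpha 10%. The success cut-off r is the smallest count with P(Bin(N, p0) ≥ r) ≤ 0.10, and power is P(Bin(N, p1) ≥ r). If k treated subjects cannot be counted as responders because of the cut-off, N stays the denominator and power becomes P(Bin(N − k, p1) ≥ r).

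| Cohort | N | p0 / p1 | r | Power stated | Power, k = 0 | Power, k = 1 |
|---|---|---|---|---|---|---|
| B1 DLBCL | 40 | 0.40 / 0.60 | 21 | 87% | 87.0% | 82.9% |
| B2 PTCL | 30 | 0.40 / 0.60 | 16 | 82% | 82.5% | 76.6% |
| B3 CTCL | 20 | 0.60 / 0.80 | 16 | 62% | 63.0% | 45.5% |
| B4 PMBL | 30 | 0.30 / 0.50 | 13 | 81% | 81.9% | 77.1% |
| B5 MGZL | 10 | 0.10 / 0.30 | 3 | 61% | 61.7% | 53.7% |

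The stated figures are reproduced to within about 1 point. The k = 1 column is the cost of losing one subject who would otherwise have had the target chance of response.

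**2. Direction.** Expected ORR falls by p1/N per lost subject: 0.60/40 = 1.5 points in B1 and 0.80/20 = 4 points in B3. With the success cut-off unchanged, the exact type I error also falls from k = 0 to k = 1: 7.4% to 5.6% in B1 and 5.1% to 2.3% in B3.

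**3. Which scans fit before the cut-off.** By the SAP convention, 8 months is 8 × 30.4375 / 7 = 34.8 weeks. Scans are planned at weeks 6, 12, 21, 30, 39 and 48, so a fixed 8-month cut-off has the first four due for everyone. Under the early trigger:

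- Cut-off before about week 6 of the last subject: that subject, and anyone else first dosed less than 6 weeks before the cut-off, may have no scan.
- Cut-off at or after the last subject's week-6 scan: nobody loses a first scan, because everyone else started earlier. Responses first seen at weeks 12, 21 or 30 can still be missed.

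**4. Illustration of the average first-scan loss.** The documents give neither accrual nor stop times, so these are assumptions: entry uniform over 18 months in each cohort, exponential stop times with median 3.5 to 5.6 months, and cut-off = last entry + min(stop time + lag, 8 months). Subjects with under 6 weeks of follow-up are lost, except that the stopping subject is not counted as lost. Mean power over 40,000 simulated trials, at medians 3.5 / 5.6 months:

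| Lag from stop to cut-off | B1 (87.0% with no loss) | B3 (63.0% with no loss) |
|---|---|---|
| None | 85.1% / 85.8% | 59.6% / 60.9% |
| 14 days | 86.2% / 86.5% | 61.4% / 62.0% |
| 35 days | 87.0% / 87.0% | 62.9% / 62.9% |

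The loss is 1.2–1.9 points in B1 and 2.1–3.4 in B3 with no lag, and 0.1 or less with 35 days. Using one last subject among all 130 instead of one per cohort gives losses of the same size.

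**The case against.** The strongest reply is that this is a wording conflict with little practical effect. Several parts of that stand.

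- The stopping subject is the first to be lost, and someone who stops all therapy before week 6 is often a true non-responder. If the stop is for progression or death, an 8-month cut-off would give the same result for that subject. A reader might take the fall from 63.0% to 45.5% in B3 as the expected effect. It is not: it applies only to a lost subject who would otherwise have had the full target chance of response. Counting the stopping subject as lost raises the no-lag illustration to 2.1–3.3 points (B1) and 4.8–7.2 (B3), which overstates the attributable loss.
- First-scan harm needs an early stop, use of the trigger and a prompt data cut. A 35-day lag removes nearly all of it.
- The assumed stop times have no source in the documents. They imply that 16–24% stop before week 6, which may be too many: single-agent continuation and treatment beyond progression are allowed, and the first scheduled scan is at week 6.
- Section 8.3.1 says approximately 8 months. That gives slack around the date, but it is not a rule tied to one subject's discontinuation.

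Two replies do not stand. SAP 6.3 defines Response Evaluable Subjects, so unscanned subjects could be identified, but SAP 7.5.1 keeps the primary ORR on all treated subjects. And a stop after week 6 is not harmless, because later first responses and follow-up are still cut short.

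**Conclusion.** The inconsistency is real and should be fixed. If the last-treated subject stops before 8 months, Section 5.4 and the other three places can give different primary data cut-offs; if that subject stays on therapy for 8 months, they agree. The trigger is unrelated to response maturity, guarantees no minimum follow-up, and does not say which last subject is meant.

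The effect on ORR is downward only. A reader might infer a raised false-positive risk from a movable cut-off; the exact calculation shows the opposite. Nor do the documents support a large or certain power loss. On the stated assumptions, with the stopping subject not counted, the first-scan loss is about 1–2 points (B1) or 2–3.5 points (B3) when data are cut on the stop date, and about 0.1 or less with a 35-day lag. Losses from responses first seen after week 6, and from shorter DOR, PFS and OS follow-up, come on top and are not quantified here.

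A reader might also suppose that every response needs a repeat scan before it counts. The documents do not establish that: Protocol 8.3.1 says confirmed, while SAP 4.1 drops the word. Only for CTCL does Appendix 4 set a duration: "All responses to be designated as CR or PR, should be documented for at least 4 weeks in duration". Because mSWAT is scored at each visit, that documentation could begin before week 6.

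Confidence is high on the textual conflict and low on the size of any loss in practice.

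**What to change.** In Protocol 5.4, delete the clause that allows an earlier analysis when the last subject discontinues. State one cut-off, in the same words, in the synopsis, 3.1, 5.4, 8.3.1 and the SAP: 8 months after the last first treatment in the cohort being analysed. This also settles which last subject is meant.

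If the sponsor wants the option of an earlier cut-off, tie it to all subjects: allow it only when every treated subject in that cohort has 8 months of follow-up, or has progressed, died, started subsequent therapy or left tumour follow-up.

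The cost is one deleted clause and one definition. At most, the analysis waits for the 8 months that the other sections already plan.
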